1.3 Study Justification

There is need for an affordable, readily available and safe method of reducing perioperative blood loss in ORIF such as TXA.

Use of TXA for this indication has not been assessed and its effect is unknown in our setting.

This study will establish the role of TXA in ORIF in a resource limited theatres. Further providing clinicians a cheap and readily available option to use in reduction of blood loss during open femur shaft fracture Intra Medullary Nailing.

Institutions like hospitals and Ministry of health can use these findings to draw up protocols and guidelines for prevention of perioperative major blood loss in patients undergoing ORIF.

The study will set a baseline on which further studies on the use of Tranexemic Acid in other orthopaedic and non orthopaedic surgical procedures may be based.

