1.6 Objectives

1.6.1 General Objective

To determine the effectiveness and safety of pre-operative intravenous Tranexemic Acid 15mg/kg on reduction of perioperative blood loss in adult patients undergoing open intramedullary nail fixation of femoral shaft fractures in Mulago National Referral Hospital.

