1.6.2.2 Secondary Objectives

1. To determine effectiveness of pre-operative intravenous Tranexemic acid 15mg/kg on reduction of transfusion rates in patients undergoing open intramedullary nail fixation of femoral shaft fractures in Mulago National Referral Hospital.
2. To determine the safety of pre-operative intravenous Tranexemic acid 15mg/kg in patients undergoing open intramedullary nail fixation of femoral shaft fractures in Mulago National Referral Hospital.

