3.1 Study design

This will be an open label single arm trial involving adult patients undergoing open intramedullary femoral shaft nail fixation at Mulago National Referral Hospital.

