3.6 Sample size estimation

3.6.1 Sampling Procedure

Comparison of Two Means (Minn M. Soe and Kevin M. Sullivan, Emory University)

$$n = \frac{(Z_1 + Z_2)^2}{(u_1 - u_2)^2} 2(S)^2$$

$$(u_1 - u_2)^2$$

n = Sample size in each group

Z₁ = 1.96 for 95% confidence level

Z₂ = 0.84 for 80% power

S = Standard Deviation of Outcome in Control Group

u₂ - u₁ = minimum meaningful difference between means

In study done in Mulago by Kajja et al estimated blood loss in 93 patient who underwent open femur shaft fracture intramedullary nailing estimated 72 hours postoperative mean total blood loss at 3.31g/dl, (SD 1.56).

Tranexemic Acid is expected to give 30% reduction in Blood Loss

i.e. $u_1 - u_2 = 0.3$

u₁

$$\underline{3.31 - u_2} = 0.3$$

3.31

$$u_1 - u_2 = 0.993$$

$$n = (1.96 + 0.84)^2 2 \times 1.56^2$$

$$0.993^2$$

$$= 38.7$$

[figure not shown]
$$n = 39$$

$$\text{Adjust for non-response} = 39 / 0.9$$

$$= 43.3 = 43$$

$$N = 43$$

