3.12 Statistical analysis

Data will then be exported into a SPSS version 19 system which will be used for analysis. We will summarise the study population. We will use descriptive statistics such as means (standard deviations) or median and interquartile range (IQR) for continuous variables and proportions for categorized variables. We will also conduct appropriate statistical tests such as chi square or Fischer's test for categorical variables and a one sample independent T-test or wilcoxon sum rank test for continuous variables.

Objective 1: *To determine the effectiveness of pre-operative intravenous Tranexemic acid 15mg/kg on reduction of perioperative blood loss as estimated by difference in 72 hour postoperative and 2 hour preoperative Hemoglobin concentration in patients undergoing open intramedullary nailfixation offemoral shaftfractures in Mulago National Referral Hospital.*

We will assess for the hypothesis that TXA reduces perioperative blood loss by at least 30% using one sample independent T-test

Objective 2: *To determine effectiveness of pre-operative intravenous Tranexemic acid 15mg/kg on reduction of transfusion rates by 30% inpatients undergoing open intramedullary nail fixation offemoral shaftfractures in Mulago National Referral Hospital.*

We will conduct univariate analysis and adjust for effect modification and confounding.

Objective 3: *To determine the safety of pre-operative intravenous Tranexemic acid 15mg/kg in patients undergoing open intramedullary nailfixation offemoral shaftfractures in Mulago National Referral Hospital.*

We will assess for safety using descriptive statistics showing proportions of adverse events in the study group.

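### The safety objective claims more than its analysis can deliver: bare adverse-event proportions in one arm of about 43 patients, with no confidence limits and no settled time window

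*Combined protocol and SAP*

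**What the plan says.** Safety is a stated objective at two levels. The general objective (section 1.6.1) begins "To determine the effectiveness and safety of pre-operative intravenous Tranexemic Acid 15mg/kg". The second of the secondary objectives (section 1.6.2.2) is "To determine the safety of pre-operative intravenous Tranexemic acid 15mg/kg in patients undergoing open intramedullary nail fixation of femoral shaft fractures", and section 3.12 repeats it as Objective 3.

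The analysis for that objective is the single sentence "We will assess for safety using descriptive statistics showing proportions of adverse events in the study group". On design, section 3.1 says "This will be an open label single arm trial involving adult patients". The sample size in section 3.6.1 rests on haemoglobin loss alone. Its "1.96 for 95% confidence level" is the Z value in that formula and the only mention of a confidence level; none is attached to an adverse-event rate.

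The definition of the safety outcome in section 3.8.2 is more modest than the objectives. It says that safety will be described through adverse events seen in the perioperative period, and it lists the events, thromboembolism among them. The stopping rules in section 3.10.3 treat safety qualitatively, and the limitations in section 3.13 do not mention sample size.

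**The concern.** A proportion from a small single arm has two weaknesses as an answer to a question about safety. There is no concurrent rate to set it against, and for an uncommon event the count may be very low or zero, in which case the point estimate says little about the risk. A reported 0% looks the same whether it comes from 40 patients or 4,000 unless limits are given.

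The proportion itself is also not fully defined, in two respects:

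- **Time window.** The operational definitions run the perioperative period from the start of surgery to 72 hours after it, and section 3.8.2 ties the safety outcome to that period. Section 3.7.7 follows patients for two weeks, and the data sheet in Appendix II has blocks for the pre/intraoperative period and for Day 3-14. An event on day 8 would be recorded, but it is unclear whether it would count.
- **Detection.** Section 3.2 says that investigation for deep venous thrombosis is not routine. Under section 3.7.7, Doppler studies follow clinical features of thromboembolism or another serious adverse event. The count is therefore of clinically detected events.

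At stake is what may properly be concluded on a stated objective. The primary result is not affected.

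**Working it through.** **Inputs.** From section 3.6.1: mean loss 3.31 g/dl, SD 1.56, difference 0.993, "1.96 for 95% confidence level" and "0.84 for 80% power". From sections 3.10.1 and 3.10.2: reviews at 50% and 90% of data collection.

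**The plan's own figure.** n = 2 × 1.56² × (1.96 + 0.84)² / 0.993² = 38.7, so 39. The step headed "Adjust for non-response" gives 39 / 0.9 = 43.3, taken as 43. Both figures reproduce. (Strict rounding up would give 44, which changes little below.)

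**Upper limit with no events.** The exact (Clopper-Pearson) two-sided 95% upper limit for 0 events in n patients is 1 − 0.025^(1/n). The one-sided 95% limit is 1 − 0.05^(1/n).

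| Patients | Two-sided 95% upper limit | One-sided 95% upper limit |
|---|---|---|
| 44 | 8.0% | 6.6% |
| 43 | 8.2% | 6.7% |
| 39 | 9.0% | 7.4% |

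At the 50% review, 43 / 2 = 21.5, so 21 or 22 patients. The two-sided limits are 1 − 0.025^(1/21) = 16.1% and 1 − 0.025^(1/22) = 15.4%. At the 90% review, 0.9 × 43 = 38.7, which is the row for 39.

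**One event.** 1/43 = 2.3%, with an exact two-sided 95% interval of 0.06% to 12.3%.

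**Chance of seeing no event in 43.** This is (1 − p)^43 for a true risk p. The documents give no background risk for these events, so the values of p are illustrations only.

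| Assumed true risk | Chance of 0 in 43 |
|---|---|
| 1% | 65% |
| 2% | 42% |
| 3% | 27% |
| 5% | 11% |

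**What an interval cannot do.** It shows the imprecision but does not reduce it. For a two-sided upper limit of 5% or 2% with no events, n = ln(0.025) / ln(1 − limit), which gives 72 or 183 patients. These targets are also illustrations and do not come from the documents.

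**The case against.** The strongest case for the plan is that its method is already descriptive. Section 3.8.2 says safety will be described, section 3.12 promises descriptive statistics, and descriptive safety reporting is usual in a study of this size. Nothing forbids an interval, which could be added at reporting from the counts in Appendix II. A data safety monitoring board oversees participants separately. All of this stands. It keeps the point modest, but it does not remove the mismatch: the objectives promise to determine safety, and no part of the plan could do that.

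Two stronger readings are tempting and should be resisted:

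- **A reader might infer that the plan would declare the drug safe if no thromboembolic event occurred.** No section sets such a rule, for zero or any other count. That would be one possible write-up, not a planned inference.
- **A reader might infer that an unsupported safety claim is meant to feed hospital or ministry guidelines.** Section 1.3 does expect the findings to inform guidelines, but on preventing major blood loss. The utility statement in the abstract concerns effectiveness. Neither says that the safety result will support a recommendation, although the findings could be read to include it.

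It is also fair to object to writing a fixed 8% into the plan. The figure depends on the confidence convention and on the number dosed, and it roughly doubles if the trial stops at the midpoint. It bounds only clinically detected events within whatever window is used. These objections stand, and the fix takes them in.

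**Conclusion.** The point holds as a mismatch between objective and analysis. Bare proportions in one arm of about 43 patients cannot support a conclusion about safety, and without limits they do not show how little they exclude. With no events, the exact two-sided 95% upper limit is 8.2% at 43 patients, 9.0% at 39 and about 16% at 21.

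The two-sided convention follows the Z value of 1.96 that the protocol uses for its sample size. The limits assume independent patients with a common risk, and they apply to events as detected under this protocol. Any statement about how many events are likely is an assumption, because the documents give no background rate.

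The documents do not support the claim that a wrong inference is planned. The change is worth making because a stated objective should not promise more than its analysis can give. It matters less than any fault in the primary analysis would.

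**What to change.** 1. In section 3.12, Objective 3, report the number of patients with at least one event over all patients actually dosed, with an exact (Clopper-Pearson) two-sided 95% confidence interval. Do this for each listed event, for any serious adverse event and for any thromboembolic event.
2. Calculate the limits from the number actually dosed at the end of the trial, including after an early stop. Do not fix a percentage in advance.
3. State the event window. Reconcile the 72-hour perioperative definition and section 3.8.2 with the two-week follow-up in section 3.7.7 and the pre/intraoperative and Day 3-14 blocks of Appendix II. If both periods are of interest, tabulate them separately.
4. Say in the plan and in the report that thromboembolic counts are clinically detected events only, and that the interval does not bound silent events.
5. Reword the objective in sections 1.6.1, 1.6.2.2 and 3.12 to describe adverse events, in line with section 3.8.2.

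This needs no extra patients, visits or tests. The cost is a column in one table, a few sentences and a less favourable safety statement.

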3.13 Study Limitations

Ward 7 theatre currently being used together with the spine team and hence reduced numbers of patients being worked on.

3.14 Ethical Considerations

The permission to carry out the study will be sought from the department of Orthopaedics, Makerere University and ethical Approval will be sought from the School of Medicine Research and Ethics Committee, Mulago Research Ethics Committee.

During the data collection, study identification numbers will be used on all study related documents to maintain confidentiality and privacy. Informed consent will be sought from all study participants before enrollment into the study.

APPENDIX I: ENROLLMENT SCREENING TOOL

Information to be picked from file of patient's with femoral shaft fractures awaiting surgery

Patient Initials: **Ward:**

Inclusion Criteria: Individual should meet all criteria to qualify for enrollment.

	Circle what applies
Duration of Injury \leq 30 days	YES / NO
Isolated Femoral Shaft Fracture	YES / NO
Patient Age \geq 18yr	YES / NO
Patient scheduled for Intramedullary Nail Fixation	YES / NO

Exclusion Criteria: Presence of any below excludes individual from enrollment.

	Circle what applies
Known Allergy to Tranexemic Acid	YES / NO
History of bleeding disorder	YES / NO
Has received or is currently on Anticoagulant therapy	YES / NO
Deep Vein Thrombosis	YES / NO
Pulmonary Embolism	YES / NO
Myocardial Infarction	YES / NO
Diabetes Mellitus	YES / NO
Pathological fracture	YES / NO

Above individual is **FIT / NOT FIT FOR ENROLLMENT**

Name of Investigator

Signature of Investigator

APPENDIX II: Data Collection Sheet

Study Number.....

Date of Surgery

Study Arm A
 B

A. Patient information

1) Inpatient number 2) Age (yrs)

3) Sex: M F 4) Weight (kg)

B. Pre-operative Data

1) Duration of Injury (Days) 2) Fracture Pattern (AO / OTA)

 A B C

3) Preoperative Hemoglobin (g/dl) 4) Platelet Count

5) aPTT 6) PT-INR

C. Procedure Data

1) Type of Anaesthesia 2) Time : Start of Surgery

GA Regional

3) Time : End of Surgery 4) Duration of Surgery (hrs)

5) Nailing Approach 6) Whole Blood Units Transfused

Ante grade / Retrograde

7) Adverse Event/s Y N (Describe Event/s)

D. Postoperative Data

1) Whole Blood Units Transfused 2) 72hr Post-operative Hemoglobin (g/dl)

3) aPTT

4) PT-INR

Peri-operative Blood Loss (g/dl)

$$= \text{Pre-opHb} - (\text{Post-opHb} + \text{Blood Units})$$

$$= \dots - (\dots + \dots)$$

$$= \dots \text{ (g/dl)}$$

Intraoperative and Post-operative Adverse Events and complications

Pre / Intraoperative Period				Comments
DVT / TEE	Nausea Vomiting Diarhoea	Anaphylaxis Dermatitis	Hypotension	
Others				
Day 1				Comments
DVT / TEE	Nausea Vomiting Diarhoea	Anaphylaxis Dermatitis	Hypotension	
Others				
Day 2				Comments
DVT / TEE	Nausea Vomiting Diarhoea	Anaphylaxis Dermatitis	Hypotension	

Others				
Day 3				Comments
DVT / TEE	Nausea Vomiting Diarhoea	Anaphylaxis Dermatitis	Hypotension Dizziness	
Others				
Day 3-14				Comments
DVT / TEE	Nausea Vomiting Diarhoea	Anaphylaxis Dermatitis	Hypotension Dizziness	
Others				

**APPENDIX III: Transfusion Guidelines for patient's participating in
“EFFECTIVENESS OF PREOPERATIVE INTRAVENOUS TRANEXEMIC
ACID ON REDUCTION OF PERIOPERATIVE BLOOD LOSS IN OPEN
INTRAMEDULLARY NAIL FIXATION OF FEMORAL SHAFT FRACTURES
IN MULAGO” Study**

Category 1	Circle	Transfusion Criteria
Intraoperative Hemoglobin Concentration of < 7g/dl	YES / NO	Transfuse with 1 Unit of WB or PRBC if 1 Criteria in category 1 is met
Category 2		
Intraoperative Hemoglobin Concentration of < 10g/dl	YES / NO	Transfuse with 1 Unit of WB or PRBC if 1 criteria in Category 2 is met together with 3 criteria in Category 3
Category 3		
Severe bleeding at the surgical site and soiling of surgical drapes and mops	YES / NO	Transfuse with 1 Unit of WB or PRBC if ≥ 4 criteria in Category 3 are met
Tachycardia	YES / NO	
Oxygen Saturation < 90%	YES / NO	
Hypotension	YES / NO	
Severe pallor of the Mucous Membranes	YES / NO	
Decreasing Levels of Consciousness	YES / NO	
Dyspnoea	YES / NO	
Angina	YES / NO	
Severe active bleeding from surgical site soiling of wound dressings with blood	YES / NO	

Re-transfusion: Reassess patient using above guidelines before next transfusion.

KEY

WB – Whole Blood

PRBC – Packed Red Blood Cells

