NDA	- NATIONAL DRUG AUTHORITY
SOMREC	- SCHOOL OF MEDICINE RESEARCH AND ETHICS COMMITTEE
TXA	- TRANEXEMIC ACID
UBTS	- UGANDA BLOOD TRANSFUSION SERVICES

ABSTRACT

Background: Major Perioperative blood loss is one of the complications of open femoral shaft fracture intramedullary nailing surgery with average blood loss estimated at 1500mls. There is need for strategies to reduce on this blood loss. Antifibrinolytics such as tranexemic acid have been successfully used to reduce perioperative blood loss in other orthopaedic procedures.

However effectiveness of tranexemic acid use during open femoral shaft fracture intramedullary nailing surgery has not been studied in our setting.

Aim: To assess the effectiveness of intravenous tranexemic acid in reduction of perioperative blood loss, transfusion rates in patients undergoing open femoral shaft fracture intramedullary nailing surgery.

Methods: This will be an open label single arm study. Patients scheduled for open femoral shaft fracture intramedullary nail fixation surgery will receive preoperative tranexemic acid at 15mg/kg. Blood loss using difference between pre and post-operative hemoglobin, blood transfusion rates and adverse events in the peri operative period will be measured.

Utility: The results of this study will reveal effectiveness of tranexemic acid in reducing perioperative blood loss during open femoral shaft fracture surgery in this setting. This information will be useful in designing protocols for prevention of perioperative blood loss for femoral shaft fracture surgery.

OPERATIONAL DEFINITIONS

Peri-operative

- Period from start of surgery to 72 hours after the Surgery

ORIF

- Open intramedullary nailing of femoral shaft fractures.

CHAPTER ONE

INTRODUCTION

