Tranexemic Acid (Kapron, Egypt) 500mg / 5ml ampoule will be used. Drug will be prepared at 15mg/kg by the anaesthetist who will administer it for over 10mins to prevent drug induced hypotension, dizziness vomiting and nausea. 10mins before skin incision so as to achieve optimal plasma and interstitial concentrations.

All patients will receive pre-operative antibiotics, before the surgery.

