3.8.2 Outcome Variables

- . Primary Outcome: Perioperative blood loss –Will be represented as difference in the 2 hour pre-operative and 72 hour post-operative hemoglobin concentration in g/dl.
- . Secondary Outcome: Blood Transfusion – will be represented as the number of blood units. 450mls of whole blood will equate to 1 unit of whole blood. 200mls of packed cells will equate to 1 unit of whole blood.
- . Secondary Outcome: Safety – Will be described as adverse events secondary to administration of Tranexemic Acid observed in patients in the study during the perioperative period.
 - Anaphylaxis
 - Dizziness
 - Hypotension
 - Nausea and Vomiting
 - Diarrhoea
 - Thrombo -embolic Events
 - Others.....

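### Appendix II prints Dizziness, a named safety outcome, only from Day 3 on, so earlier dizziness is recorded without a named prompt and may be under-counted

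*Combined protocol and SAP*

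**What the plan says.** Section 3.8.2 defines the secondary safety outcome: "Will be described as adverse events secondary to administration of Tranexemic Acid observed in patients in the study during the perioperative period". The list beneath it names dizziness alongside anaphylaxis, hypotension, nausea and vomiting, diarrhoea, thrombo-embolic events and others. The operational definitions give the perioperative period as "Period from start of surgery to 72 hours after the Surgery".

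Section 3.7.3 gives the reason for infusing over 10 minutes: "to prevent drug induced hypotension, dizziness vomiting and nausea". The plan thus treats dizziness as a possible effect of the infusion.

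Section 3.12, Objective 3, gives the whole safety analysis: "We will assess for safety using descriptive statistics showing proportions of adverse events in the study group".

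Appendix II collects these events in five blocks: "Pre / Intraoperative Period", Day 1, Day 2, Day 3 and Day 3-14. In the first three, the fourth cell reads hypotension alone. In the last two it reads "Hypotension Dizziness". Each block also has an Others row and a Comments column. Separately, item C7 under Procedure Data reads "Adverse Event/s Y N (Describe Event/s".

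**The concern.** A named item on a form makes staff ask about it; an unnamed one has to be volunteered or noticed. Here the prompt is missing from the block that covers the infusion and from the next two days, and present in the two blocks furthest from the dose. Objective 3 is purely descriptive and the trial has one arm, so no concurrent group shares the same recording gap. The form's content therefore bears directly on the reported proportion.

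At stake is one secondary safety figure: the proportion of patients with dizziness, and whether its early and late components can be read side by side. A smaller issue sits in the same table. Day 3 belongs to two rows, and Day 3 is about where the 72-hour window closes.

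**Working it through.** There is no plan figure to reproduce. The check is a block-by-block reading of Appendix II against the outcome list in section 3.8.2.

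| Block | DVT/TEE | Nausea, vomiting, diarrhoea | Anaphylaxis, dermatitis | Hypotension | Dizziness | Others and Comments |
|---|---|---|---|---|---|---|
| Pre/Intraoperative | yes | yes | yes | yes | **no** | yes |
| Day 1 | yes | yes | yes | yes | **no** | yes |
| Day 2 | yes | yes | yes | yes | **no** | yes |
| Day 3 | yes | yes | yes | yes | yes | yes |
| Day 3-14 | yes | yes | yes | yes | yes | yes |

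1. **Prompting.** Dizziness is printed in 0 of the 3 blocks before Day 3 and in 2 of the 2 blocks from Day 3 on. Every other printed term is in 5 of 5.
2. **Within the outcome window.** The safety outcome runs to 72 hours, roughly the first four blocks. Dizziness is prompted in 1 of those 4.
3. **Other routes.** Free text is possible in all five blocks, and C7 adds a yes/no question with a description for the procedure. None of these names dizziness.
4. **Size.** Let *k* be the number of patients whose only dizziness is before Day 3, and *r* the share of them recorded in free text. The recorded count is *k* × *r*, which lies anywhere from 0 to *k*. The documents give neither *k* nor *r*. At the planned N = 43 (section 3.6), each patient missed lowers the proportion by 1/43 = 0.023, or 2.3 percentage points. Nothing in the documents takes the calculation further.
5. **Row overlap.** An event on Day 3 can be entered under Day 3, under Day 3-14, or both. If it is entered only under Day 3-14, the row label does not show whether it belongs to the 72-hour outcome.

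**The case against.** The strongest reply is that the form does not prevent early recording. Item C7 asks a direct adverse-event question about the procedure, and every block takes free text. Section 3.7.7 has patients reviewed daily by the investigator, surgeons and residents. Section 3.7.6 lists dizziness among the signs to weigh in transfusion decisions, so staff already have reason to notice it. This stands, and it limits the point to unequal prompting.

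A second reply is that the text may be faulty. The blocks without the word all come before an apparent page break, and those with it come after. Loss in extraction from the PDF cannot be excluded. Against that, the same single word is missing three times beside intact cells, so an artefact is unproven. The source PDF should settle it.

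Third, a patient under general anaesthesia cannot report dizziness during surgery, so a printed item would recover nothing there. That is fair, but it does not explain the gap on Days 1 and 2, or under regional anaesthesia, which the form also allows.

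Finally, double entry of a Day 3 event would not change a per-patient proportion if each patient is counted once. That also stands; the overlap matters for placing the event in time.

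**Conclusion.** The form, as extracted, prompts a named safety outcome unevenly. Dizziness before Day 3 may be under-counted by an amount the documents do not allow to be sized, and counts are not comparable across periods. The Day 3 overlap is real but small. The conclusion assumes that the extracted table matches the source, and that a named item is recorded more completely than an unnamed one. The issue is minor: one descriptive secondary safety item, with no bearing on the primary outcome or the sample size.

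A reader might infer more, but the documents do not support these stronger readings:

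- **Early dizziness would be reported as zero.** This holds only if entries under C7, Others and Comments are discarded. Section 3.12 does not restrict the proportions to printed items, and section 3.8.2 includes an others category.
- **The reported figure will mostly reflect Days 3 to 14.** Days 4 to 14 lie outside the 72-hour safety outcome, and no expected counts are given for any period.
- **The dose would cause dizziness on Day 1 or Day 2.** Section 3.7.3 links dizziness to the infusion; nothing extends that effect to later days.

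**What to change.** First check Appendix II in the source PDF. If the table is as extracted:

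- Print the same adverse-event list, including Dizziness, in all five blocks, matching section 3.8.2.
- Relabel the last block Day 4-14, so that each day belongs to one row.
- State in section 3.12 that each patient is counted once per event type in the 72-hour safety proportions, and that entries under C7, Others and Comments are included.

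The cost is a one-page form edit and one sentence in the analysis section, with no extra visits or tests. It is best done before the form is first used, because a prompt not given at the time cannot be recovered later.
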